We are proposing a prospective, randomized, two-arm, open label pilot study to demonstrate the in vivo effects previously seen in preclinical studies using cervical cancer cell lines16-20. Study participants will be recruited from the Grady Cancer Center of Excellence and the Infectious Disease Program at Grady's Ponce Clinic. A convenience sample of 40 HIV uninfected and infected participants with biopsy-proven HSIL will be randomized to one of two arms (2000 mg of curcumin powder in capsules or placebo inserted intravaginally weekly at bedtime for 12 weeks, (excluding the time when they are on their menses) as demonstrated in the schema.

Cervical cytology, vaginal swabs, colposcopies and biopsies will be performed every 4 weeks during each study visit for the study duration for the primary objectives outlined in specific aims 1-3. These time points were selected to acquire cervical samples prior to treatment, during treatment and 4 weeks after treatment completion (LEEP specimen). Study drug and placebo will be administered during weeks 1-12 (12 weeks of treatment) and no treatment will be administered during weeks 13-16 (washout period). Cervical biopsies will be performed in areas with a colposcopic suggestion of HSIL disease and four additional cervical punch biopsies (one specimen from each of four quadrants) of the cervix will be done for downstream biomarker analysis. The laboratory, pathology and data analysis staff will be blinded to treatment arm. The clinicians performing the colposcopies nor the participants will not be blinded secondary to the evident color of curcumin.

Study Population

HIV uninfected and infected women will be recruited for this study. We will focus only on HIV infected women without an AIDS defining disease, given that the risk of progression from high grade lesions to invasive carcinoma is faster in HIV infected subjects who are significantly immune compromised.

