All study subjects will be instructed to insert 2000 mg total curcumin capsules at bedtime every week. The study subject will place four 500 mg Curcumin C3 Complex® capsules into the opening of the vaginal applicator and insert the capsules using the applicator while lying on their back with their knees bent (Figure 1). The subject will be instructed to gently inserted the capsules into the vagina as far as it will go

comfortably (Figure 1), similar to a tampon insertion or other common intravaginal drugs (fungal treatments). All required capsules should be inserted at one time. After successful insertion of the capsules, the subject will remove the vaginal applicator for disposal. The study subject who is randomized to the gelatin capsules will insert the placebo capsules in the same manner as the study drug. [name] holds the FDA IND (no.103,496) for the intravaginal use of curcumin for human clinical trials.

Figure 1. Insertion of study drug

Dosing regimen

2000 mg total (4 capsules) of curcumin powder in capsules or placebo inserted intra-vaginally weekly at bedtime for 12 weeks, (excluding the time when they are on their menses).

Treatment Plan

There is no concern about progression of cervical intraepithelial lesion (CIN) 3 disease or severe dysplasia within the time course of this study (4-5 months) based on the natural history of CIN 3 (severe cervical dysplasia). Approximately 30% will regress and 50-70% will progress to cancer however the rate of progression to cancer takes 5-10 years to occur. Though the data of the natural history of cervical dysplasia was in HIV uninfected women; data from the Women Interagency HIV study has also reported that in a well followed cohort of HIV infected women, rates of invasive cervical cancer was the same in HIV infected women as in HIV uninfected women. We expect the same outcomes in both cohorts of women.

In addition time, course to cancer is not significantly faster to require treatment to occur sooner than their HIV negative counterpart. Presently, HIV positive young women with histologic HSIL disease (CIN 2,3) are now offered in clinical practice active monitoring with colposcopies every 6 months instead of treatment of cervical dysplasia to avoid the negative pregnancy outcomes from treatment. This change in practice is due to the number of HIV positive women desiring fertility and pregnancy and the effectiveness of HAART in pregnancy.

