Enrolled subjects will be asked to agree to the use of reliable birth control: Combined oral contraceptive pill (OCP), Long Lasting Reversible Contraceptive (LARCP), Bi-Lateral Tubal Ligation (BLT) and Depo-Provera Shot/Birth control shot and they will be given a partner notification letter advising them to use a condom when having vaginal sex with their partner and the risks associated with lack of use of a condom.

Clinical care practice guidelines indicate colposcopy every 6 months. We will be following these subjects every month with colposcopy for research purposes of this study, which is more than sufficient to clinically monitor and capture any women at risk for progression of disease. Subjects will be informed that the alternative to this study or if disease progression occurs, is referral for continued clinical care with their provider where they will this they will discuss the treatment (Leep with continued active monitoring-colposcopy with biospies) with their provider at the Grady Cancer Center of Excellence treatment Clinic or at the Emory Clinic.

Randomization Method

The treatment assignments will be generated with the use of a pseudo-random-number generator with randomly permutated blocks that will be used to ensure balance between the number of subjects assigned to each treatment (1st: 2000 mg of curcumin for 12 weeks versus placebo capsules for 12 weeks). Before the study starts, the Pharmacist at Ponce Clinic (IDP) or Grady CRN will be sent a batch of sealed, sequenced, opaque envelopes containing the treatment assignment. The envelopes will have a unique ID consisting of a sequence number determining the treatment arm. Once informed consent is obtained on a subject, the Study Coordinator/P.I. will set up an appointment for the screening visit at the Ponce clinic (IDP) or Grady CRN to confirm clinical eligibility. Once the participant is cleared to enter the study, they will be given a unique ID associated to the batch of envelopes in the care of the Grady CRN or Ponce Clinic (IDP) Pharmacist.

Subject Recruitment:

All subjects will be recruited from Grady Cancer Center of Excellence at Grady Memorial Hospital (GMH) and the Grady Infectious Disease clinic at Ponce (IDP) per the inclusion and the exclusion criteria below.

Inclusion Criteria:

- 1. Age 21 years and older
- 2. HIV uninfected and infected women (without AIDS defining illness)
- 3. HSIL cytology with no invasive features identified on colposcopy or the baseline biopsy

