- 4. Compliant on combined anti-retrovirals (cART) if HIV infected
- 5. On continuous antiretrovials with CD4 count >200 cells/ml with sustained undetectable viral load for at least 3 months. (HIV positive women)
- 6. Patient on reliable (OCP, LARC, BTL or Depo Provera) birth control: Combined oral contraceptive pill (OCP). Long Lasting Reversible Contraceptive (LARCP), BiLateral Tubal Ligation (BLT) and DepoProvera Shot/Birth control shot.
- 7. Patient willing to conform to the study requirements
- 8. No risk factors for microinvasive disease (no colposcopic features of microinvasion, adequate colposcopy and negative endocervical curettage)

Exclusion Criteria:

- 1. Age over 21 years of age
- 2. Invasive features on colposcopy and the biopsy specimen
- 3. Not compliant with anti-retroviral therapy (cART) (HIV infected participants)
- 4. CD4 count <200 cells/ml and detectable viral load within the least 3 months (HIV infected participants
- 5. Lactating and pregnant women
- 6. Patient with irregular cycles (more than once a month).
- 7. Patient not on reliable birth control.
- 8. Previous hysterectomy and/or prior treatment for cervical precancer condition

Study visits

Subjects that are eligible and volunteer to take part, they will be asked to do the following:

- A. Sign the combined ICF/HIPAA Authorization Form and a medical release form.
 - a. Update their contact information.
- B. Respond to Questionnaires
- C. Undergo a thorough medical evaluation at their screening visit. This will include
 - i. Review of their medical records
 - ii. Medical history obtained by study personnel
 - iii. Physical examination by study personnel.
 - iv. Have urine take for a pregnancy test at each visit.
 - v. Receive a pap smear
 - vi. Vaginal sampling.
- D. Use a reliable form of birth control and keep a pill diary for the duration of the study.
- E. Place the four capsules, (curcumin or placebo), into the vagina at bedtime during the course of the study.
- F. Undergo cervical sample collection, colposcopy, and cervical biopsy during study visits (every 4 weeks).
- G. Give their partner sign a notification letter that informs them of the study and the precautions to be taken during vaginal sex while their partner is in the study.
- H. Undergo LEEP procedure.
- I. Respond to phone contact twice a week

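### Exclusion 1 contradicts inclusion 1 on age; as a secondary inconsistency, the eligibility list does not carry the biopsy-proven HSIL that the design section describes

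*Combined protocol and SAP*

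**What the plan says.** **Age.** Inclusion Criteria, item 1: "Age 21 years and older". Exclusion Criteria, item 1: "Age over 21 years of age". The Subject Recruitment section says that all subjects are recruited according to these two lists.

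**Disease status.** Research Design and Methods: "A convenience sample of 40 HIV uninfected and infected participants with biopsy-proven HSIL will be randomized to one of two arms". Inclusion Criteria, item 3: "HSIL cytology with no invasive features identified on colposcopy or the baseline biopsy". Exclusion Criteria, item 2: "Invasive features on colposcopy and the biopsy specimen". The Treatment Plan shows that the protocol recognises histologic HSIL as a distinct entity, since it refers to "HIV positive young women with histologic HSIL disease (CIN 2,3").

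**Where the lists are used.** Under Randomization Method, a woman cleared to enter the study is given an ID tied to the assignment envelopes. Under the Data and Safety Monitoring Plan, monitors may check eligibility.

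**The concern.** The two age rules cannot both operate as intended: the exclusion removes nearly everyone whom the inclusion admits. This is an internal inconsistency in the operative criteria, not in background text. A site or monitor applying the list as written would record a deviation for every woman older than 21.

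The second issue is smaller. The design section describes a histologically defined population, but the list that staff apply defines it by cytology. A woman can satisfy every criterion and still not belong to the population described in the design section. Specific Aim 1 is framed around HSIL lesions, so the report should be able to say which definition the enrolled women met.

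**Working it through.** The plan gives no figure on eligibility, so the check is mainly logical.

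**1. Age.** Let A be age in completed years.
- Inclusion 1 admits {A ≥ 21}.
- Exclusion 1 removes {A > 21}.
- Eligible: {A ≥ 21} minus {A > 21} = {A = 21}.

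| Age | Meets inclusion 1 | Meets exclusion 1 | Result |
|---|---|---|---|
| 20 or less | no | no | out |
| 21 | yes | no | eligible |
| 22 or more | yes | yes | out |

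The complement of inclusion 1 is {A < 21}. With that as exclusion 1, the eligible set becomes {A ≥ 21} minus {A < 21} = {A ≥ 21}, and the conflict disappears.

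**2. Does any other text correct it?** No. The other mentions of age concern cancer and its precursors in wider populations (Summary) or current practice in young women with HIV (Treatment Plan). Neither sets an age for participants.

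**3. Is it a slip?** Almost certainly. Two other exclusions are exact negations of an inclusion. Exclusion 3, "Not compliant with anti-retroviral therapy (cART) (HIV infected participants"), negates inclusion 4, "Compliant on combined anti-retrovirals (cART) if HIV infected". Exclusion 7 negates inclusion 6 on birth control. Exclusion 1 appears to have been meant in the same way. Exclusions 2 and 4 resemble inclusions 3 and 5 but are not exact negations. Negating inclusion 3 gives invasive features on colposcopy *or* biopsy, whereas exclusion 2 joins them with *and*. Negating inclusion 5 gives a CD4 count not above 200 *or* detectable virus, whereas exclusion 4 again uses *and*. So the exact pairs are two, not four.

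**4. Histology.** There are 8 + 8 = 16 criteria.
- Naming HSIL: 1 (inclusion 3, by cytology).
- Naming a biopsy: 2 (inclusion 3 and exclusion 2), both to rule out invasion.
- Inclusion 8 adds colposcopy and curettage, to rule out microinvasion.
- Requiring HSIL on biopsy: 0.

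The design section and the list can both be true of the same woman, but meeting the list does not imply biopsy-proven HSIL.

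**5. Endpoint and sample size.** The rationale for Specific Aim 1 says that E6/E7 is assayed on liquid-based cytology samples, so the primary endpoint can be measured whichever entry definition applies. The power statement (20 per arm, ratio 1.536, coefficient of variation 0.5, two-sided 0.05) reproduces on the log scale:
- log SD = √ln(1 + 0.5²) = 0.4724
- difference = ln(1.536) = 0.4292
- standardised effect = 0.4292 / 0.4724 = 0.909
- noncentral-t power = 0.7995, against the stated 80%

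None of these inputs depends on the wording at issue.

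**The case against.** On age, the best reply is that the intent is plain, nobody is likely to apply the literal reading, and monitors only may check eligibility. The intent is indeed plain, and that limits the practical risk. It does not remove the defect, because the error is in the list that governs recruitment and no other text overrides it.

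On histology, the reply is stronger. The design section is itself protocol text, so the intended entry status is documented even though the list does not repeat it. The two statements do not exclude each other, and the primary endpoint does not use biopsy tissue. All of this stands, and it is why the histology point is secondary.

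A reader might infer three stronger things that the documents do not support:
- **That power is lost to women without histologic HSIL.** This would need the rate at which HSIL cytology is not confirmed on biopsy, and the treatment effect in such women. The documents give neither.
- **That women will be found ineligible after randomisation**, because the first scheduled study biopsies fall at the baseline visit, where medication is also dispensed. Screening includes a review of medical records, so an earlier diagnostic biopsy may be what is meant. The schema figures are also not shown.
- **That exclusion 1 follows a pattern of four mirrored pairs.** Only exclusions 3 and 7 are exact complements.

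**Conclusion.** The age contradiction is an error as written. Taking age in completed years, the eligible set is age 21 only, and every enrolment at 22 or older is a deviation on the literal text. It is almost certainly a slip, but one that needs correcting.

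The histology mismatch is a lesser inconsistency: 0 of 16 criteria require the biopsy-proven HSIL that the design section attributes to the 40 randomised women. It would be tempting to say that the eligibility list is wrong in two places. The documents do not support that, because a cytologic entry rule is compatible with the design statement and could be what the sponsor wants. The two texts are simply not aligned. No number of affected women can be given, and no effect on power, sample size or measurement of the primary endpoint is claimed.

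**What to change.** 1. Reword exclusion 1 as the complement of inclusion 1, so that it excludes women below 21. This is a one-word change.
2. Reconcile Research Design and Methods with inclusion 3 so that both state the same entry definition: cytologic, histologic or both. The choice is the sponsor's.

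The cost is a few lines in a protocol amendment. Neither change alters the sample size or the analysis.

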Although clinical studies have shown that curcumin is safe and well tolerated with no significant toxicity and an acceptable blood chemistry profile, its use is limited by its low systemic bioavailability (9, 10, 14, 15, 17). To circumvent this problem, we administered curcumin capsules through an intravaginal approach and tested safety, tolerability and acquired pharmacokinetic data. We found no severe adverse events or dose limiting toxicities during our phase I trial of 13 subjects treated daily for 14 days with intravaginal curcumin (appendix 1). Three subjects (1 taking 1000 mg dose, 2 taking 1500 mg dose) completed 13 of the 14 days, with the reason for non-compliance being they chose not to finish. In addition, curcumin and curcumin conjugates were not measurable in the serum, and detectable concentrations were not observed in the urine of study participants (presented at Eurogin 2011). With a low side effect profile, easy application, and low cost, this potentially therapeutic herb can be sustainable in low resource countries. We are also supported by a recent study from India conducted by Basu(10) et al 2013. Their study clearly demonstrated that intravaginal curcumin is safe and tolerable. The main reason for the

discontinuation of the drug was vulvovaginal irritation and itching. This application explores the effect of topical application of curcumin as a potential chemoprevention agent in the suppression of cervicovaginal HPV infection and subsequent risk for cancer of the cervix. IND #103496 is in place to proceed with this study.

SPECIFIC AIMS

This application explores the effect of curcumin, a known chemotherapeutic agent as a potential medical treatment in HIV uninfected and infected women (without AIDS defining illness) with high grade squamous intraepithelial lesions (HSIL) of the cervix. We plan to address our specific aims by conducting a pilot two-arm study in which women will be randomized to 2000 mg of intravaginal curcumin versus placebo weekly for 12 weeks.

The specific hypothesis of this phase II study is that intravaginal curcumin will decrease expression of HPV oncogenic biomarkers associated with cervical cancer and this will correlate with the levels of curcumin detectable in the cervical tissue.

Specific Aim 1 (Primary Objective):

Determine the association between intravaginal curcumin on known HPV-related molecular target HPV E6/E7 mRNA expression within HSIL lesions of the cervix in HIV uninfected and infected women.

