
Rationale:

The HPV E6/E7 oncoproteins have significant roles in malignant transformation and are consistently expressed in malignant cervical tissue. Increasing levels of E6 and E7 expression cause genetic instability, and implies a risk for cellular changes, which results in a selective growth advantage (31, 34-37). The APTIMA® HPV Assay that we will be utilizing in our studies detects full-length HPV E6/E7 mRNA for HPV types 16, 18, 31, 33, 35, 39, 45, 51, 52, 56, 58, 59, 66, and 68 and correlates very well with integrated HPV, which in turn correlates with full-length HPV E6/E7 protein levels (38).

All methodologies for evaluating the expression and function of HPV E6/E7 are ongoing in the laboratory of the co-investigator ([name]) and are described in referenced publications (27-34). The expression of HPV E6/E7 proteins will be assessed by the APTIMA* HPV Assay using liquid-based cytology specimens.

Specific Aim 2 (Secondary Objective):

To quantify levels of curcumin in the cervix of women in the curcumin treatment arm.

Rationale:

To date, there are no published data on the tissue penetration of curcumin in vivo. This will establish the level of curcumin penetration in cervical tissue as well as the cumulative effect of weekly curcumin over time. This study will establish the baseline which is crucial in designing further curcumin intervention studies. The methodology of curcumin measurement for this study is well documented in Subhashini et al (16).

Specific Aim 3 (Exploratory Aim):

To determine the association between curcumin and other known biomarkers of cervical disease and its effect on the vaginal microbiome.

Rationale:

To determine the most relevant duration for curcumin treatment, as well as identify additional biomarkers that are regulated with the pharmacological activity of curcumin, we will measure mRNAand/or protein expression levels of p16INK4a, p53, Rb, VEGF and NF-κB in cervical biopsy specimens. A combination of immuno-histochemical methods and other molecular assays (RT-PCR, ELISA, TransAM NF-κB DNA binding ELISA) to determine mRNA levels and protein levels on transcription factor binding activity will also be done.

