A speculum will be inserted into the vagina to visualize the cervix. A sample of cells from the outer opening of the cervix is collected with a plastic cytobroom/endocervical brush which is rotated in the central opening of the cervix. The cells are placed on in liquid media (SurePath) and ThinPrep (HPV) and taken to the laboratory to be checked for abnormalities /cervical disease and HPV.

1.3 Follow up:

Subjects will be contacted within 48 hours after the start of the medication to inquire on any issues affecting your adherence to the study medication after the baseline visit.

Subjects will receive a call twice a week from week 4 through week 16 to inquire on any issues affecting your adherence to the study medication.

All women will be contacted by telephone to discuss all cytology and histology results and Cytology and histology results will be available for all study participants PCP if a medical release waiver is signed by the subject. We will be following these subjects every month with colposcopy which is more than sufficient to capture any women at risk for progression and they will be referred to treatment is progression of disease occurs.

- 2 Laboratory Evaluations
- 2.1 Pap and HPV testing will be performed by Grady pathology lab.
- 2.2 The APTIMA® HPV Assay (HPV viral load quantitative/ Detection of HPV mRNA Levels)

The Aptima HPV assay offers a unique screening approach by targeting high-risk human papillomavirus (HPV) mRNA from the E6/E7 oncogenes. The Aptima HPV assay offers the same excellent sensitivity and improved specificity as compared to DNA-based tests. The expression and function of HPV E6/E7 a will be conducted in the lab of [name].

STATISTICAL ANALYSIS:

Aim1: To determine the association between intravaginal curcumin on known HPV-related molecular target HPV E6/E7 mRNA expression within HSIL lesions of the cervix in HIV uninfected and infected women. Biomarkers are known to be differentially regulated in cervical disease. Current literature shows that HPV E6/E7 mRNA, NF-kB, p16INK4a and VEGF levels are up-regulated, whereas p53 levels are down-regulated in cervical disease. Biomarker outcome, defined as the level of mRNA and/or protein in the samples collected, will be summarized with standard descriptive statistics and represented graphically with displays such as box plots by treatment group. For this study the biomarkers whose levels will be quantified are as follows:

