- Primary endpoints: Human papillomavirus E6/E7 (HPV E6/E7)
- Secondary endpoints: NF-κB, p16INK4a, Rb, p53 and VEGF.

HPV E6/E7 mRNA testing has been demonstrated to be a useful tool in the diagnosis of cervical cancer prevention and will be the primary end-point for this aim. The primary objective for this study is to look at the association between curcumin and cervical disease. In vitro work shows that curcumin treatment inhibits the transcription of HPV E6/E7, thus restoring the expression of proteins such as p53 and that over expression of HPV E6/E7 is a good indicator of risk and progression to cancer. (Maher DM, 2011 Jan;50(1)). Collectively the vitro and our in vivo findings may show that curcumin should be considered an effective chemopreventive and therapeutic agent for cervical cancer prevention and treatment.

Aim2: To quantify levels of curcumin in the cervix of women in the curcumin treatment arm. The mean tissue concentration of curcumin in the cervix at each time point (baseline, 1,2,3,4, and 5 months) will be calculated. This secondary objective quantifies the pharmacologically active levels of curcumin recovered from cervical tissue, for information to be gathered on the levels of curcumin that is absorbed into the cervical tissue and thus eliciting a direct pharmacological effect.

Aim 3: To determine the association between curcumin and other known biomarkers of cervical disease. This exploratory aim seeks to use repeated-measures analyses, utilizing a linear mixed model for the curcumin group to assess the association between and each biomarker (NF-kB, p16INK4a, Rb, p53 and VEGF) and the concentration of curcumin at each time point (baseline, 1, 2, 3, 4, and 5 months).

The primary analysis will be conducted with a two sample two sided t-test to compare the each of the primary endpoints and secondary endpoints, between the two arms of the study, those on treatment (curcumin capsules) and those on the placebo, respectively. If normality cannot be assumed a Wilcoxon rank-sum test will be used instead. Chi-square test or Fisher's exact test will be used to compare categorical characteristics by treatment group.

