Acceptability Questionnaires: Descriptive statistics on subject and partner responses from the acceptability questionnaires will be reported.

Power and sample size calculation: The expression of E6/7 is the primary endpoint of the study and will be used in the power and sample size calculation with a two sample two sided t-test. In this study, we will enroll 20 patients in each of the two groups. Therefore, the group sample sizes of 20 in Curcumin group and 20 in placebo group will achieve at least 80% power at the significant level of 0.05 to detect a difference of a ratio of 1.536 or higher in the expression of E6/ between the two groups, assuming the coefficent of variation is 0.5.

SAFETY EVALUATION:

Adverse Events (AEs) and Serious Adverse Events (SAEs)

This investigational agent is studied under IND # 103496 and monitoring will be performed per previously agreed upon FDA guidance.

There may be some minor irritation from the intravaginal curcumin to the vaginal mucosa and staining of underwear. Other side effects which can happen include the upset stomach, diarrhea, burning sensation in the vagina, dizziness, insomnia, rash, pruritus generalized, and fever. The literature shows that over 13 subjects in United States and 151 subjects in India (10) have been studied with curcumin without any serious adverse effects.

Our phase I study has shown that curcumin is safe in dosage up to 2000mg.

Any patient intervention related adverse effects, an unanticipated problem, or reportable protocol deviation/ non-compliance will be reported to the Emory IRB office according to IRB P & P and to the FDA according to regulations.

Any serious adverse effects will be communicated by the principal investigator to the Emory IRB using the standard adverse event reporting forms.

SAEs will be defined per FDA standards and include those that result in death, are life threatening, result in a disability, cause for hospitalization, or to a congenital abnormality or birth effect. SAEs will be reported to the DSMC, IRB and FDA and manufacturer as required.

CLINCAL OUTCOMES AND MEASURES:

The table below gives the descriptions to be used to document findings during colposcopy.

| Colposcopic findings | | | | Presence | |
|----------------------|----------------------|----------------------|----------------------|----------|--------|
| | Grade 1 | Grade 2 | Grade 3 | | |
| | (Mild) | (Moderate) | (Severe) | Present | Absent |

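### The primary E6/E7 variable is not uniquely defined, and the plan does not establish that the assay gives the continuous level its t-test and power statement need

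*Combined protocol and SAP*

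**What the plan says.** **What is measured.** Specific Aim 1 names "HPV-related molecular target HPV E6/E7 mRNA expression within HSIL lesions of the cervix in HIV uninfected and infected women", and the Statistical Analysis section repeats this. The rationale under Specific Aim 1 says instead: "The expression of HPV E6/E7 proteins will be assessed by the APTIMA* HPV Assay using liquid-based cytology specimens". The same rationale says that this assay "detects full-length HPV E6/E7 mRNA for HPV types 16, 18, 31, 33, 35" and further types. The heading of section 2.2 under Laboratory Evaluations labels the assay "HPV viral load quantitative/ Detection of HPV mRNA Levels". The Statistical Analysis section defines the biomarker outcome as a level of mRNA, protein or both. It lists the primary endpoint simply as HPV E6/E7, then refers to mRNA testing as the primary endpoint.

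**How the assay is described.** Section 2.2 presents it as a screening approach and gives its performance as "The Aptima HPV assay offers the same excellent sensitivity and improved specificity as compared to DNA-based tests". The protocol text gives no unit, normalisation, limit of quantification or rule for undetectable samples.

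**How it is analysed.** "The primary analysis will be conducted with a two sample two sided t-test", with a Wilcoxon rank-sum test if normality cannot be assumed. No transformation is mentioned. Chi-square and Fisher tests are named for categorical characteristics. The power paragraph claims at least 80% power, with 20 per arm at the 0.05 level, "to detect a difference of a ratio of 1.536 or higher in the expression of E6/ between the two groups", assuming a coefficient of variation of 0.5.

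**The concern.** mRNA, protein and viral load are different quantities, and a lesion and a liquid-based cytology sample are different specimens. From this text a statistician could not construct the primary variable without further decisions, and those decisions might be made after data are seen.

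The analysis also presupposes something the assay description does not supply. A ratio between arms and a coefficient of variation have meaning only for a positive continuous measurement. If the laboratory returned only detected or not detected, the planned t-test would not suit the endpoint and the power statement would not apply. A 1.5-fold fall in mRNA could then leave every woman positive and be read as no effect.

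Even with a numeric readout, two matters stay open. The scale of the t-test is not stated. The eligibility criteria do not require detectable E6/E7 mRNA at entry, so undetectable values can occur, and these have no logarithm.

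**Working it through.** **1. Reproduce the stated power.** Inputs from the power paragraph: n = 20 per arm, two-sided 0.05, ratio 1.536, CV 0.5. Assume lognormal data with the same CV in both arms.

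- SD of the log value = √ln(1 + 0.5²) = √ln(1.25) = 0.472
- Difference on the log scale = ln(1.536) = 0.429
- Standardised difference = 0.429 / 0.472 = 0.909
- Noncentrality = 0.909 × √(20/2) = 2.87, with 38 degrees of freedom
- Power by the noncentral t distribution = 79.95%

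The ratio that gives exactly 80% is 1.5364, so the stated figure is correct to rounding. The other variants tried do not match:

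| Variant | Power |
|---|---|
| One-sided 0.05 | 88.0% |
| Log-SD taken as 0.5 | 75.3% |
| Raw difference 0.536 with SD 0.5 | 91.0% |

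Of these variants, only the two-sided log-scale calculation gives the stated figure.

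**2. The t-test as written, without transformation.** Lognormal data were simulated with the same inputs (log-SD 0.472, log difference 0.429, 20 per arm, 400,000 trials). Testing the log values gives 80.0%, which agrees with step 1. Testing the untransformed values gives 75.7%, or about 76%. The gap is about 4 percentage points.

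**3. If the readout were only detected/not detected (illustration).** The documents give no positivity rate, so every control rate here is an assumption. Power is for the two-sided Fisher exact test at 0.05 with 20 per arm, summing binomial probabilities over all tables.

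| Assumed control positivity | Curcumin positivity for about 80% power | Curcumin positivity if the 1.536 ratio applied to positivity | Power at that ratio |
|---|---|---|---|
| 100% | about 68% | 100/1.536 = 65.1% | 88% |
| 95% | 56% | 95/1.536 = 61.8% | 67% |
| 90% | 47% | 90/1.536 = 58.6% | 53% |

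For the first row, 69% gives 79.1% power and 68% gives 81.7%.

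**The case against.** The strongest reply is that the plan clearly intends a quantitative outcome. The section 2.2 heading uses the word quantitative. The Statistical Analysis section says that levels will be quantified and plans box plots. Routine Pap and HPV testing (2.1) is listed separately from the E6/E7 work. The rationale for Specific Aim 1 leaves E6/E7 methods to a co-investigator's laboratory and cited publications, where a unit and normalisation may be given. Sensitivity and specificity do not exclude a numeric output, since a quantitative assay with a cut-off has both.

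All of this stands, and it limits the point. A reader might infer from the screening and accuracy language that the assay is positive/negative, and hence that the t-test is wrong and the power claim void. The documents do not support that: no sentence says the E6/E7 readout is qualitative. Nor do they support a claim that the sample-size arithmetic is wrong, because it reproduces for a lognormal level.

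The reply does not remove the inconsistency. Intending to quantify does not define a variable, and the rationale names protein as what an mRNA assay will measure. The protocol text itself leaves unit, scale, specimen and handling of undetectable values open.

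**Conclusion.** The point holds as a defect of definition in the only powered endpoint. The analyte and specimen are described inconsistently, and the documents do not establish the positive continuous level that the primary test and power statement require.

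If a continuous level exists, the size is modest: 79.95% power on the log scale against about 76% untransformed, assuming lognormal data with CV 0.5 in both arms and no loss of patients. If the readout proves to be only detected/not detected, the effect could be larger and would depend on control positivity. Applying the 1.536 ratio to positivity, power runs from 88% at an assumed 100% control rate to 53% at 90%. Those figures are contingent on an unconfirmed readout and are not a finding about this trial's power.

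**What to change.** 1. Define the primary variable once, as E6/E7 mRNA level, with its unit and normalisation. Correct the reference to proteins in the Specific Aim 1 rationale and to viral load in the section 2.2 heading.
2. Reconcile the specimen: lesion tissue or liquid-based cytology.
3. Specify the primary t-test on log-transformed values, reported as a ratio with a 95% confidence interval, and state a rule for undetectable samples. This matches the scale on which the power figure reproduces.
4. Have the sponsor confirm the assay readout in writing before analysis. If only detected/not detected is available, make the primary analysis a Fisher exact comparison of positivity, with a risk difference and exact 95% confidence interval, and replace the power statement with detectable differences for stated control rates.

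Cost: items 1 to 3 are protocol and SAP wording if a quantitative readout already exists. A binary readout would mean a less favourable stated detectable difference. Neither route needs extra patients or visits. Moving the endpoint to another quantitative method, such as the RT-PCR planned for other markers on biopsies, would be laboratory work and might change the specimen, so it should not be treated as a wording change.
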